- b. Symptoms must have been present for at least 60 days prior to screening. Symptoms that wax and wane must have been initially present at least 60 days prior to screening.

AND

- c. Symptoms must be reported to be at least somewhat bothersome and to have an impact on quality of life and/or everyday functioning.

5. Long COVID attributed to a SARS-CoV-2 infection prior to August 15, 2022. Note: While individuals re-infected with SARS-CoV-2 after August 15, 2022 will not be excluded, the SARS-CoV-2 infection after which Long COVID symptoms began must pre-date August 15, 2022.

6. Not currently hospitalized.

7. Body mass index (BMI) 18 to 50 kilograms/meter squared (kg/m^2), inclusive, at the time of screening.

8. In otherwise stable health, as assessed by the investigator within 28 days prior to Screen, based on medical history, physical assessment, laboratory findings, and vital signs.

9. Participants who are of childbearing potential (CBP) and male participants with sexual partner(s) who are females of CBP must agree to use adequate contraception from study consent through 360 days after dosing. Adequate contraception is defined as using hormonal contraceptives or an intrauterine device combined with at least 1 of the following forms of contraception: a diaphragm, a cervical cap, or a condom. Total abstinence from vaginal intercourse, in accordance with the lifestyle of the participant, is also acceptable.

10. Willingness and ability to comply with the study protocol. This includes reliable transportation and sufficient time to attend all visits.

11. Written informed consent (and assent when applicable) obtained from subject or subject's legal representative and ability for subject to comply with the requirements of the study.

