### 9.1.6 Questionnaire-based Measurements

**Medical History Questionnaires.** As part of the medical history at the Screening Visit, participants may be assessed for several medical conditions thought to be related to Long COVID. These may include questions or checklists about chronic fatigue symptoms, hypermobility symptoms, endometriosis symptoms (ENDOPAIN-4D scale) and mast cell activation syndrome (Mast Cell Activation Questionnaire).

**Long COVID Symptom Assessment.** Signs and symptoms related to Long COVID will be reviewed at all visits, using the LIINC CRFs. This will include the presence and absence of Long COVID symptoms within the prior 30 days and the prior 2 days, as well as information about how bothersome the symptoms are. Long COVID symptoms are one of the primary outcomes of the study.

**Other Symptom Assessment (AE Review).** In addition to Long COVID symptoms, at D0 and all subsequent visits, all grades of signs and symptoms that are newly developed or changed since the previous visit will be recorded. Symptoms not previously experienced as part of Long COVID, or which have worsened beyond the degree previously experienced by the participant, will be considered to represent adverse events and recorded as such. For these symptoms, duration (start and stop dates), severity/grade, outcome, treatment, and relation to study drug will be recorded on the case report forms. All clinical events and new diagnoses or changes in diagnoses should be recorded.

**Quality of Life.** Quality of life (QoL) will be obtained using a scale such as the EQ-5D-5L scale which is part of the LIINC CRFs. This will include the 100-point visual analogue scale (VAS).

**PROMIS-29.** The PROMIS-29 form will be completed as outlined in the schedule of events. This scale measures self-reported health, using a collection of short forms assessing fatigue, physical function, anxiety, depression, pain, sleep disturbance, and ability to participate in social roles and activities. The questionnaire uses a computer interface over approximately 5 minutes. It is available in English and Spanish. This instrument has been used for ME/CFS and Long COVID.

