#### 9.1.7 Adverse Events

Information regarding occurrence of adverse events will be captured throughout the study. Duration (start and stop dates), severity/grade outcome, treatment and relation to study drug will be recorded on the case report form (CRF).

This is a study of Long COVID symptoms. As a result, symptoms experienced prior to receipt of the study intervention will be documented, and a symptom will only be considered to represent an AE if its quality or severity differs from or exceeds that which was previously experienced by the participant.

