## **10.2 Baseline Evaluation (D-7)**

An additional visit will be performed following Screening, at least 7 days after the screening visit and prior to D0. The target date for this visit is within 7 days prior to the scheduled date of study product administration, although up to 21 days is acceptable. The purpose of this visit is to make additional assessments prior to the intervention, to establish baseline symptomatology and measurements. This will include a symptom assessment and various clinical assessments as outlined in the Schedule of Events. Certain real-time laboratory tests will be obtained to establish a baseline.

If needed to reduce participant burden (at the request of the participant or investigator team) the assessments from the Baseline Visit may be conducted over two visits during the baseline period, but all Baseline assessments must be completed prior to the day of the infusion visit.

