### **11 ADVERSE EXPERIENCE REPORTING AND DOCUMENTATION**

#### **11.1 Adverse Events**

An adverse event (AE) is any untoward medical occurrence in a clinical investigation of a patient administered a pharmaceutical product, which does not necessarily have a causal relationship with the treatment. An AE is therefore any unfavorable and unintended sign (including an abnormal laboratory finding), symptom or disease temporally associated with the administration of an investigational product, whether or not related to that investigational product. An unexpected AE is one of a type not identified in nature, severity, or frequency in the current Investigator's Brochure or of greater severity or frequency than expected based on the information in the Investigator's Brochure.

**Suspected Adverse Reaction (SAR)** - any AE for which there is a reasonable possibility that the drug caused it. It implies a lesser degree of certainty about causality than **adverse reaction** (any AE caused by a drug).

An unexpected AE or unexpected SAR is one of a type not identified in nature, severity, or frequency in the current Investigator's Brochure or of greater severity or frequency than expected based on the information in the Investigator's Brochure.

The Investigator will probe, via discussion with the subject, for the occurrence of AEs during each subject visit and record the information in the site's source documents. Adverse events will be recorded in the patient CRF. Adverse events will be described by duration (start and stop dates and times), severity, outcome, treatment and relation to study drug, or if unrelated, the cause.

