## APPENDIX 1. SCHEDULE OF EVENTS

Target Day	-28	-7	0	1	15	30	90	180	360
Visit Name	Screen	Baseline	Intervention	Phone FU	2W	1M	3M	6M	12M
Visit Window	-28 to -8	-21 to -1	N/A	+1	+/-3	+/-5	+/-14	+/-14	+/-28
Screening Procedures									
Informed Consent	x								
Eligibility Review	x								
Screening Labs	x								
Demographics	x								
Medical History (inc. ME/CFS, hEDS, EM, MCAS assess.)	x								
COVID-19 History	x								
Concomitant Medications	x	x	x	x	x	x	x	x	x
Study Product Administration									
Randomization			x						
AER002 vs Placebo			x						
Clinical Assessments									
Vital Signs	x	x	x 		x	x	x	x	x
Physical Assessment	x	PRN	PRN		PRN	PRN	PRN	PRN	PRN
Long COVID Symptom Assessment (LIINC Quest.)	x	x	x		x	x	x	x	x
Quality of Life, (e.g., EuroQoL)	x	x			x	x	x	x	x
PROMIS-29	x	x			x	x	x	x	x
PGIC Scale						x	x	x	x
Duke Activity Status Index	x	x			x	x	x	x	x
Post-COVID Functional Scale	x	x			x	x	x	x	x
Dysautonomia Assessment (e.g., COMPASS-31)		x					x	x	x

Target Day	-28	-7	0	1	15	30	90	180	360
Visit Name	Screen	Baseline	Intervention	Phone FU	2W	1M	3M	6M	12M
Visit Window	-28 to -8	-21 to -1	N/A	+1	+/-3	+/-5	+/-14	+/-14	+/-28
DSQ-PEM		x		x	x	x	x	x	x
WHO-DAS		x					x	x	x
Neurocognitive assessment (e.g., NIH Toolbox)		x					x	x	x
6MWT		x			x	x	x	x	x
Safety Outcomes									
AE Review	x	x	x	x	x	x	x	x	x
Safety Labs			x		x				
Real-time laboratory tests									
Pregnancy testing	x		x				x		
Complete metabolic panel	x		x		x				
CBC/diff	x		x		x				
Coagulation studies Within 6 months of Screen	x								
Hep B surface antigen Within 6 months of Screen	x								
Hep C antibody Within 6 months of Screen	x								
Hep C RNA (if Ab positive) Within 6 months of Screen	x								
Plasma HIV RNA (if HIV+) Within 2 months of Screen	x								
C-reactive protein		x	x		x	x	x	x	x
Erythrocyte sedimentation rate		x	x		x	x	x	x	x
D-dimer		x	x		x	x	x	x	x
Fibrinogen		x	x		x	x	x	x	x
SARS-CoV-2 PCR or Ag test	x	PRN	PRN		PRN	PRN	PRN	PRN	PRN
Stool collection (optional)		x				x		x	x

Target Day	-28	-7	0	1	15	30	90	180	360
Visit Name	Screen	Baseline	Intervention	Phone FU	2W	1M	3M	6M	12M
Visit Window	-28 to -8	-21 to -1	N/A	+1	+/-3	+/-5	+/-14	+/-14	+/-28
Post-hoc laboratory tests									
SARS-CoV-2 antibody testing		x							
Biospecimen storage	x	x	x		x	x	x	x	x
Markers of viral persistence	x	x	x		x	x	x	x	x
Markers of inflammation		x	x		x	x	x	x	x
PK analyses 			x 		x	x	x	x	x

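### The rule for counting Long COVID symptoms as adverse events does not name the pre-infusion state as its comparator, so a return to an earlier severe level may be left out of the primary safety count

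*Combined protocol and SAP*

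**What the plan says.** The primary outcome (protocol 5.2, SAP 2.3 and SAP 5) is the number of participants per arm with an AE of Grade 3 or higher judged at least possibly related to treatment. It therefore depends on what counts as an AE.

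- **Protocol 9.1.6 (AE Review)** first has staff record signs and symptoms that are new or have changed since the last visit. It then gives AE status to "Symptoms not previously experienced as part of Long COVID, or which have worsened beyond the degree previously experienced by the participant".
- **Protocol 9.1.7** puts a similar limit on any one complaint: it "will only be considered to represent an AE if its quality or severity differs from or exceeds that which was previously experienced". The same sentence says that "symptoms experienced prior to receipt of the study intervention will be documented".
- **Protocol 11.1** has the general definition, which includes "any unfavorable and unintended sign (including an abnormal laboratory finding), symptom or disease temporally associated with the administration of an investigational product". It has no exclusion for symptoms seen earlier and no reference to 9.1.6 or 9.1.7.
- **Protocol 10.2** says that the Baseline visit serves "to establish baseline symptomatology and measurements". Appendix 1 schedules the Long COVID symptom assessment at Screening, Baseline and Day 0, and at every in-person follow-up visit.
- **Inclusion criterion 4b** admits fluctuating disease: "Symptoms that wax and wane must have been initially present at least 60 days prior to screening".
- **SAP 2.3 and 5** list treatment-emergent AEs but do not define them.

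**The concern.** Keeping ordinary fluctuation of the disease under study out of the AE tables is reasonable. The difficulty is that the comparator is not fixed. What was previously experienced could mean the whole course of the illness, or the state documented before infusion. The two differ for a participant who was once severely affected, had improved by Day 0, and relapsed after infusion to the earlier level but no further.

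That participant is foreseeable, because criterion 4b admits symptoms that come and go. Protocol 2.3.1 also lists new or worse symptoms after infusion among the possible side effects, and several of those it names, such as tiredness and difficulty breathing, overlap with qualifying Long COVID symptoms. Safety is the primary objective and the primary results are meant to be descriptive, so in a trial of 20 versus 10 one or two classifications change what is reported. If the drug provoked such relapses, the uncounted cases would fall mainly in the active arm and make it look safer.

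**Working it through.** The documents state no figure on this point, so there is none to reproduce. The check is a comparison of the texts, followed by an illustration of scale.

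**1. One constructed case under each text.** Suppose fatigue was Grade 3 earlier in the illness and Grade 1 at Day 0. At Day 15 it is Grade 3 again, with the same quality, and is judged possibly related.

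| Text | Comparator: whole illness | Comparator: Baseline/Day 0 |
|---|---|---|
| 9.1.6 (new, or beyond the earlier degree) | Not new, and 3 does not exceed 3: no AE | 3 exceeds 1: AE |
| 9.1.7 (quality or severity differs or exceeds) | Same quality, same earlier severity: no AE | Severity differs: AE |
| 11.1 (general definition) | AE | AE |

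So 9.1.6 and 9.1.7 give opposite answers depending on the comparator, and 11.1 gives one answer throughout. No passage says which comparator applies or which section governs.

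**2. Conditions for a loss.** All of these must hold: an earlier Grade 3 or higher level; improvement by Day 0; a return to that level but not beyond it; unchanged quality; a judgement of at least possibly related; and site staff applying the whole-illness reading. The documents give no frequency for any of them.

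**3. Scale, by assumption.** Arms are 20 and 10 (protocol 8.1). Assume that 1 or 2 AER002 participants go uncounted and that neither arm has any other qualifying event.

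Agresti-Coull 95% interval (SAP 5), with z = 1.96: n' = 20 + 3.84 = 23.84; p' = (x + 1.92)/23.84; limits p' ± 1.96·√(p'(1 − p')/n'), cut at 0.

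- x = 0: p' = 0.0806, upper limit 0.190
- x = 1: p' = 0.1225, limits 0 to 0.254
- x = 2: p' = 0.1645, limits 0.016 to 0.313

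The Clopper-Pearson interval in protocol 15.3 gives a similar picture: 0/20 upper limit 16.8%; 1/20 0.1% to 24.9%; 2/20 1.2% to 31.7%.

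Agresti-Caffo 95% interval for the risk difference against 0/10 (SAP 3.3): p1 = (x + 1)/22; p2 = 1/12; limits (p1 − p2) ± 1.96·√(p1(1 − p1)/22 + p2(1 − p2)/12).

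- x = 0: −21.7 to 14.1 points (observed difference 0)
- x = 1: −19.0 to 20.5 points (observed difference 5.0)
- x = 2: −15.9 to 26.5 points (observed difference 10.0)

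Two-sided Fisher test against 0/10: 1/20 gives p = 1.00. For 2/20, the chance that both fall in the active arm is 190/435 = 0.437 and that both fall in placebo is 45/435 = 0.103, so p = 0.54. Significance would need 8/20 (p = 0.029), since 7/20 gives p = 0.064. The counts and intervals move; the test result does not.

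**The case against.** The strongest reply is that the text leans towards the pre-infusion comparator. Protocol 9.1.7 joins the documenting of pre-infusion symptoms and the AE test in one sentence, and it accepts a difference in severity, not only an excess. The AE rule in 9.1.6 directly follows the instruction to record change since the previous visit. The symptom form looks back 30 days and 2 days, and no worst-ever severity is described, so the whole-illness reading would rest on recall. An investigator could also rely on 11.1. This stands as far as it goes: it makes the loss uncertain. It does not settle the matter, because recording a change is not the same as classing it as an AE, and the wording in 9.1.7 still compares with an undated earlier experience.

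The rule also applies to both arms, and the site staff who apply it are blinded. That limits differential judgement, but it does not restore events that the rule leaves out.

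A reader might infer more than the documents support in two ways.

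- **That SAEs and committee triggers are equally exposed.** Both are built on AEs, so the possibility exists, but it is remote. Protocol 9.1.6 separately asks for all clinical events to be recorded, and 11.2.1 requires all SAEs to be documented whatever their cause. A lost Grade 4 event would need an earlier Grade 4 symptom in someone who was in stable health at screening.
- **That a relapse would go unseen in the arm comparison.** The SAP compares PROMIS-29, EQ-5D, DASI, COMPASS-31, WHO-DAS and PGIC by arm as primary or secondary efficacy outcomes, and DSQ-PEM and the symptom form as exploratory ones. A general worsening could show there. What those analyses do not give is a count of participants who returned to a severe level.

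**Conclusion.** The point holds in a limited form. The AE rule for Long COVID symptoms has no stated comparator, it is not reconciled with the general definition, and the SAP does not fill the gap. On the plain wording of 9.1.6, a related Grade 3 or greater return to an earlier level, after improvement by Day 0, may be left out of the primary safety count. A reader might conclude that such events will be missed. The documents do not show that, because they also allow the reading under which the events count.

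The size is unknown. Under the assumed one or two uncounted AER002 participants and no other events, a report of 1/20 or 2/20 becomes 0/20, and the Agresti-Coull upper limit falls from 25.4% or 31.3% to 19.0%. The Fisher result does not change. Priority: minor.

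**What to change.** 1. Cross-reference 9.1.6, 9.1.7 and 11.1, and state that treatment emergence of a Long COVID symptom is judged against the symptom status documented at Baseline/Day 0. Say which of the two visits governs if they differ.
2. Define TEAE in the SAP on the same basis.
3. Report by arm, in a category separate from new events, the participants whose existing Long COVID symptoms worsened from that reference to Grade 3 or greater, where a grade was recorded.

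Grades may be missing for changes that were not classed as AEs, since 9.1.6 limits the detail as follows: "For these symptoms, duration (start and stop dates), severity/grade, outcome, treatment, and relation to study drug will be recorded on the case report forms". A table built instead from ungraded scales, such as the bothersomeness item, DSQ-PEM or PROMIS-29, should have its threshold fixed before unblinding. It should be labelled exploratory and not a substitute for the Grade 3 count, because those scales are not toxicity grades.

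The cost is wording in three protocol sections, one SAP definition and one table, with no new visits. If data collection is complete, only the SAP definition and the table remain. The downside is more background events from natural fluctuation in both arms. The separate category keeps these apart from new events, and the blinded placebo arm shows how common they are without the drug.

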#### 9.1.7 Adverse Events

Information regarding occurrence of adverse events will be captured throughout the study. Duration (start and stop dates), severity/grade outcome, treatment and relation to study drug will be recorded on the case report form (CRF).

This is a study of Long COVID symptoms. As a result, symptoms experienced prior to receipt of the study intervention will be documented, and a symptom will only be considered to represent an AE if its quality or severity differs from or exceeds that which was previously experienced by the participant.

### 9.1.8 Infusion-related Site Reactions (IRSRs)

The following system will be used to grade IRSRs:

Infusion reaction to IV IP	None (0)	Mild (Grade 1)	Moderate (Grade 2)	Severe (Grade 3)	Potentially Life Threatening (Grade 4)
Pain (Note: Pain is perceived by the subject without touching.)	No pain	Does not interfere with activity	Repeated use of non-narcotic pain reliever > 24 hours OR interferes with activity	Any use of narcotic pain reliever OR prevents daily activity	Emergency room (ER) visit or hospitalization
Tenderness (Note: Tenderness is pain or discomfort when an affected body part is palpated or moved. It is possible to have both pain & tenderness.)	No tenderness	Mild discomfort to touch	Discomfort with movement	Significant discomfort (guarding) at rest  Note: Subject may avoid moving OR limits movement of affected area	ER visit or hospitalization
Erythema (Redness)	No erythema	2.5 – 5 cm	5.1 – 10 cm	> 10 cm	Necrosis or exfoliative dermatitis
Induration*	No induration	2.5 – 5 cm and does not interfere with activity	5.1 – 10 cm or interferes with activity	> 10 cm or prevents daily activity	Necrosis

Edema**	No edema	2.5 – 5 cm and does not interfere with activity	5.1 – 10 cm or interferes with activity	> 10 cm or prevents daily activity	Necrosis
Pruritus (itch)	No pruritus	Mild pruritus. Does not interfere with activity	Repeated use of anti-pruritic medication > 24 hours OR interferes with activity	Prevents daily activity	ER visit or hospitalization
Accompanying sensory symptoms: Burning, tingling, and/or stinging	None	Mild sensory symptoms. Does not interfere with activity	Interferes with activity	Prevents daily activity	ER visit or hospitalization

\*Skin induration is a deep thickening of the skin that can result from edema, infiltration, or inflammation. Diagnosis of skin induration is made by palpation and assessing whether the affected area has a hard resistant feeling.

\*\*Edema is an abnormal buildup of fluid in the body; swelling

Reference: Table modified from Guidance for Industry. Toxicity Grading Scale for Healthy Adult and Adolescent Volunteers Enrolled in Preventive Vaccine Clinical Trials. September 2007. US Department of Health and Human Services (HHS), Food and Drug Administration (FDA), Center for Biologics Evaluation and Research (CBER).

#### 9.1.9 Participants with Positive COVID Tests During the Study

Due to the ongoing pandemic, it is anticipated that some individuals may test positive for COVID-19 during the course of the study.

If an individual tests positive for SARS-CoV-2 infection on a clinical swab during the screening procedures, they will not be eligible to participate unless [REDACTED] is performed and confirmed to demonstrate a variant susceptible to AER002.

If an individual exhibits acute COVID-19 symptoms during the study, we will arrange for or navigate to testing. If an individual tests positive for SARS-CoV-2 during the course of the study, we will leverage existing testing and treatment programs in our hospital system and/or geographic region to navigate the participant to care. In addition to navigation for clinical care, all participants who test positive during the study will be referred to a home-based research collection protocol for more frequent sampling (see Appendix 3).

## **9.2 Clinical Laboratory Measurements**

### **9.2.1 Hematology**

Blood will be obtained and sent to each site's clinical hematology lab for a complete blood count (hemoglobin, hematocrit, red blood cell count, white blood cell count, white blood cell differential, and platelet count), erythrocyte sedimentation rate (ESR), and serum C-reactive protein (CRP) determinations for assessment of systemic evidence for infection and/or inflammation. These measurements will be performed as outlined in the Schedule of Events.

### **9.2.2 Blood Chemistry Profile**

Blood will be obtained and sent to each site's clinical chemistry lab for determination of serum sodium, potassium, chloride, bicarbonate, random glucose, BUN, creatinine, aspartate aminotransferase (AST/SGOT), alanine aminotransferase (ALT/SGPT), alkaline phosphatase, total bilirubin, direct bilirubin, and albumin. These measurements will be performed as outlined in the Schedule of Events.

### **9.2.3 Coagulation Studies**

Coagulation studies will be performed at Screening, unless a PT-INR and PTT are available within the prior 6 months. Additional coagulation studies, including D-Dimer and Fibrinogen levels, will be performed as part of the study outcome measurements.

